- The test result is considered to be an adverse event by the investigator or the sponsor Simply needing to repeat an abnormal test, in the absence of the above conditions, does not constitute an adverse event. Any abnormal test result that turns out to be due to an error does not need to be reported as an adverse event.

Serious adverse events

A serious adverse event is defined an unwanted medical effect occurring in a patient receiving a medication or nutritional product, regardless of the dose, that:

- Leads to death
- Is life-threatening
- Requires hospitalisation of the patient or prolongs a hospitalisation (see below for the circumstances in which this does not constitute an adverse event)
- Leads to a persistent or significant incapacity (substantial disruption to the ability to conduct acts of daily living)
- Leads to a congenital anomaly or birth defect

Progression of the malignancy over the course of the study (including signs and symptoms of progression) must not be reported as a serious adverse event, unless this results in death during the study or during the adverse events notification period. Hospitalisation due to the signs and

final version of 17/07/2018

symptoms of disease progression must not be reported as a serious adverse event. If the malignancy results in death during the study or adverse events notification period, then the event leading to death must be recorded as an adverse event, and as a grade 5 serious adverse event.

An event will be defined as a medically important event on the basis of medical and scientific judgement. A medically important event is not immediately life-threatening and/or does not lead to death or hospitalisation. However, if it is established that the event may jeopardise the patient and/or require an intervention in order to avoid the outcomes outlined above, the medically important event must be reported as serious.

For example, this category of medically important events would include allergic bronchospasm requiring intensive care in the emergency department or at home, blood dyscrasias, convulsions that do not lead to hospitalisation, or even the development of dependence on a medication or abuse of a medication.

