It is important to note that statistical comparisons in the strictest sense between the different treatment groups in this observational study are not appropriate due to the expected bias and because the groups are not comparable at enrolment (treatments not assigned randomly). If, however, comparisons are envisaged, a multivariate Cox model will be used in order to adjust for patient characteristics that may potentially be associated with the type of treatment received and survival and that could be liable to skew the estimates (confounding factors, effect modification).

 Safety of the treatments (targeted therapies and other treatments) during the prospective phase of the study, defined by instances of treatment discontinuation and the reasons for this, adverse events (graded according to the 'Common Terminology Criteria for Adverse Events' (CTCAE) version 4.0 of May 2009), and any complications of adverse events.

The proportion of patients for whom adverse events are reported (total proportion and proportion reporting grades 3 or 4 adverse events) will be estimated as well as the proportion who stop treatment due to an inability to tolerate it.

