Treatment	Start date	Date stopped	If stopped, reason	
		definitively		
Treatment ongoing at previous visit	Start date	- If stopped, date	If stopped, Reason	
(auto)	(auto)	stopped	☐ Disease progression	
			☐ AE	
		- If not, Ongoing.	If AE, has an AE reporting	
			form been completed?:	
			☐ Yes ☐ No	
			If no, please report the AE*	
			☐ Patient's decision	
			☐ Doctor's decision, if so	
			please state why:	
			☐ Cumulative dose reached	
			☐ Scheduled stop	
			☐ Optimum response☐ Other, please state:	
			☐ Other, please state:	
			Lost to follow-up	
			☐ Death → redirects to the	
			Anticipated end of study	
			questionnaire	
Targeted therapy	/ /	- If stopped, date	If stopped, Reason	
everolimus		stopped	☐ Disease progression	
sunitinib		/ /	☐ AE	
Chemotherapy		- If not, Ongoing.	If AE, has an AE reporting	
□ 5 FU		, , , ,	form been completed?	
☐ Capecitabine (Xeloda®)			☐ Yes ☐ No	
☐ Doxorubicin (Adriamycin®)			If no, please report the AE*	
☐ Streptozocin (Zanosar®)			☐ Patient's decision	
☐ Temolozomide (Temodal®)			☐ Doctor's decision, if so	
☐ Dacarbazine (Deticene®)			please state why:	
☐ Oxaliplatin (Eloxatin®)			☐ Cumulative dose reached	
☐ Gemcitabine (Gemzar®)			☐ Scheduled stop	
□ Cisplatin			Optimum response	
□ VP-16			☐ Other, please state:	
Other, please state:			District fallows	
Somatostatin analogues Octreotide			☐ Lost to follow-up	
☐ Lanreotide			☐ Death → redirects to the	
Interferon alpha			Anticipated end of study questionnaire	
☐ Interferon alpha			questionnaire	
Radionuclide therapy				
☐ Radionuclide therapy				
Other				
☐ Other, please state:				
(lines may be added if there are more tr	eatments to enter)			
* If there has been an adverse event, p	lease complete the	safety section of the CRF	within the stated timeframe	
If no "ongoing" treatment is entered of	and if the patient is	s not deceased or lost to	follow-up (will be checked by the	
eCRF):				
Is the patient receiving a new treatmer			-	
If yes, please describe the new treatmen	nt line targeting the	tumour that was put in pl	ace at today's visit (see Table 5)	
If not, the following is displayed:	udu la aat at 3	ara Diagga rangas sha fa	llow up visit at the most town	
The patient follow-up phase in the st assessment visit.	uuy is set at 2 ye	ars. Frease repeat the 10	now-up visit at the next tumour	
מססכססווופווג עוסול.				
For each line of cancer treatment enter	ed, the participatin	g doctor will be redirected	d to the corresponding screen.	

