3.4 Safety – onset of adverse events
Has the patient experienced adverse events since the last documented visit on [date of last tumour assessment]
visit entered]? ☐ Yes ☐ No
If yes, please describe all adverse events experienced in the Safety section of the eCRF (see 5. Adverse events recording module)
4. Anticipated end of study form
STATUS OF PATIENT
☐ Alive date of last contact: ☐ / ☐ / ☐ (DD/MM/YYYY) Main reason for stopping the study
Does not meet the inclusion criteria at enrolment - exclusion
□ Patient's decision
☐ Transferred to another treatment centre not participating in the study
Other reason, please state:
□ Lost to follow-up date of last contact: □□/□□/(DD/MM/YYYY)
□ Deceased*
◆ If deceased, please state Date of death
Study medication(s) at the time of death
□ Sunitinib
□ Everolimus
☐ Octreotide ☐ Other treatment, please state:
☐ Chemotherapy
☐ Interferon alpha
☐ Somatostatin analogue other than Octreotide
☐ Radionuclide therapy
Cause of death
☐ Disease progression ☐ Adverse event* not related to a study medication
☐ Adverse event* related to a study medication
,
*Places complete the reference tion of the CDF
*Please complete the safety section of the CRF TREATMENT ONGOING WHEN PATIENT LAST SEEN
THEATMENT ONGOING WHEN FAMILY EAST SEEN
If the anticipated end of study form is completed at a time other than a follow-up visit:
Therapeutic management between the last documented tumour assessment visit on [date of the last documented
visit] and up to the anticipated end of study date:
→ Display section 3.3 Therapeutic management since last tumour assessment
→ Display Table 5 and the screens corresponding to each recorded treatment line
DISEASE OUTCOME

Novartis Pharma S.A.S. - Pfizer S.A.S

Page 85 of 90

Observational study protocol $final\ version\ of\ 17/07/2018$

Best response to treatment when patient	last seen	
☐ Complete response	☐ Stable disease	
☐ Partial response	☐ Disease progression	
Date of the last disease assessment: \\ \\ \ \ \ \ \ \ \ \ \ \ \ \ \ \ \ \		

Please complete the adverse events table for all events reported since inclusion in the study: Description of the adverse event: Table 4 - Safety											
Description the event		Date onset	of	Outcome	Severity	CTCAE grade	Seriousn ess	Causality of the study treatment	Action concerning the study treatment		
History of	pre	viously	des	cribed adverse events	s						

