5.7.2. Adverse Events

The numbers and percentages of patients with the following characteristics will be shown overall, and by group at inclusion during the study (targeted therapy/other treatments). We will also show the results by treatment being received at the time of inclusion and during the study: everolimus/sunitinib/chemotherapy/somatostatin analogs etc.

- at least one adverse event,
- at least one serious adverse event,
- at least one adverse event with a suspected relationship with the study treatment,
- an adverse event which was fatal,
- at least one adverse event resulting in permanent discontinuation of treatment,
- at least one adverse event resulting in dosage adjustment/temporary discontinuation of treatment.

- at least one adverse event with a suspected relationship with the study treatment leading to permanent discontinuation of the treatment,
- at least one adverse event with a suspected relationship with the study treatment leading to a dosage adjustment/temporary discontinuation of treatment,
- at least one serious adverse event with a suspected relationship with the study treatment leading to permanent discontinuation of the treatment,
- at least one serious adverse event with a suspected relationship with the study treatment leading to a dosage adjustment/temporary discontinuation of treatment.

The same information will be produced for grade ≥ 3 adverse events.

The following information will also be shown:

- at least one grade 3 adverse event,
- at least one grade 3 serious adverse event,
- at least one grade 3 adverse event with a suspected relationship with the study treatment,
- at least serious grade 3 adverse event with a suspected relationship with the study treatment,
- at least one grade 4 or higher adverse event,
- at least one grade 4 or higher adverse event with a suspected relationship with the study treatment.

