For combination treatments, the start and end date of the combination were not recorded in the CRF. The visit immediately before the report of the additional combination will therefore be deemed to be the start date and the visit corresponding to discontinuation of the combination will be deemed to be the end date of the combination, unless the combination began or finished during a treatment line (where start and end dates are reported). The 28-day rule also applies to combination treatments.

The AEs will be analysed as follows:

	Actual exposure	Actual exposure +28 days	Treatment reported in the "Causality with the study treatment" column
At least one adverse event		X	
At least one serious adverse event		X	
At least one adverse event with a suspected relationship with the study treatment			X
At least one adverse event resulting in death		X	
At least one adverse event leading to permanent discontinuation of treatment	X		
At least one adverse event leading to change in dosage/temporary discontinuation of treatment	X		
At least one adverse event with a suspected relationship with the study treatment leading to permanent discontinuation of treatment	X		X
At least one adverse event with a suspected relationship with the study treatment leading to adjustment of dosage/temporary discontinuation of treatment	X		X
At least one adverse event with a suspected relationship with the study treatment leading to temporary discontinuation of treatment	X		X
At least one serious adverse event with a suspected relationship with the study treatment leading to permanent discontinuation of treatment	X		X
At least one serious adverse event grave with a suspected relationship with the study treatment leading to adjustment of dosage/temporary discontinuation of treatment	X		X
At least one serious adverse event with a suspected relationship with the study treatment leading to temporary discontinuation of treatment	X		X

^{*} AEs on treatment analysed as reported in the actual exposure and in the "causality with the study treatment" column.

Adverse events will be listed overall, together with the grade ≥ 3 adverse events, serious adverse events, adverse events with a suspected relationship to the study treatment leading to permanent discontinuation of the treatment and adverse events with a suspected relationship to the study treatment leading to temporary discontinuation of the treatment.

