5.9.5. Discontinuation Due to Toxicity

Discontinuation due to toxicity (AE or death) of the main treatment line will be described for the period after inclusion. The number of patients with at least one discontinuation due to toxicity and the number of discontinuations due to toxicity will be described based on:

- The main treatment ongoing at inclusion (Targeted therapy (of any kind, then Everolimus and Sunitinib), Chemotherapy, Somatostatin analog).
- Number of lines for the entire follow-up (≤ 2 lines, ≥ 2 lines).
- Number of targeted therapies received for the entire follow-up (0, 1, 2, >2).
- Targeted therapy received as 2nd line main treatment vs Chemotherapy received as 2nd line main treatment for the entire the follow-up period.

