9.3.4. Discontinuation Due to Toxicity

Table 14.2.2.4.1: Discontinuation Due to Toxicity During Follow-Up (Post Inclusion) – Reference Set – Subgroup Analysis Based on the Number of Main Treatment Lines Throughout Follow-Up (≤2 Lines, >2 Lines)

		≤2 lines (N = XX)	>2 lines (N = XX)	Total (N = XX)
Patients who have discontinued at least once due to toxicity*	N	XX	XX	XX
	Missing data	XX	XX	XX
	Yes	XX (XX.X%)	XX (XX.X%)	XX (XX.X%)
	No	XX (XX.X%)	XX (XX.X%)	XX (XX.X%)
If yes, number of discontinuations per patient due to toxicity**	N	XX	XX	XX
	Missing data	XX	XX	XX
	Mean (SD)	XX.XX (X.XX)	XX.XX (X.XX)	XX.XX (X.XX)
	Mean	XX.X	XX.X	XX.X
	[Min; Max]	[XX.X; XX.X]	[XX.X; XX.X]	[XX.X; XX.X]
	[Q1; Q3]	[XX.X; XX.X]	[XX.X; XX.X]	[XX.X; XX.X]
	1			
	2			
	3			

^{*} Discontinuation due to toxicity corresponds to discontinuation for an AE or Death.

Using the same template:

Table 14.2.2.4.2: Discontinuation Due to Toxicity During Follow-Up (Post Inclusion) – Reference Set – Subgroup Analysis Based on the Number of Targeted Therapies Received Throughout Follow-Up (0, 1, 2, >2)

Table 14.2.2.4.3: Discontinuation Due to Toxicity During Follow-Up (Post Inclusion) – Reference Set – Subgroup Analysis Based on the Number of Patients Having Received Targeted Therapies as a 2nd Line and Patients Having Received Chemotherapy as a 2nd Line Throughout Follow-Up

^{**} A patient may record several discontinuations due to toxicity.

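### The SAP's 'discontinuation due to toxicity' counts treatment stops coded Death whatever the cause, so a tumour death coded that way is reported as toxicity in Tables 14.2.2.4.1 to 14.2.2.4.3

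*SAP*

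**What the plan says.** SAP 5.9.5 states: "Discontinuation due to toxicity (AE or death) of the main treatment line will be described for the period after inclusion". It asks for the number of patients with at least one such stop and the number of stops, by treatment at inclusion, number of lines, number of targeted therapies received, and second-line targeted therapy versus second-line chemotherapy. The footnotes to Table 14.2.2.4.1 (SAP 9.3.4) and Table 14.3.1.7 (SAP 9.4.1) give the same definition: "Discontinuation due to toxicity corresponds to discontinuation for an AE or Death". The scope is main treatment lines after inclusion in the first table and the treatment at inclusion in the second.

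The CRF appended to the protocol keeps the reasons apart. In its Table 5 (Therapeutic management), disease progression, AE and Death are different tick-boxes for why a line was stopped. Ticking Death ("Death → redirects to the" end-of-study questionnaire) sends the investigator to the form that records the cause of death. That form (CRF section 4) offers three causes: disease progression, "Adverse event* not related to a study medication", and an adverse event related to one.

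**The concern.** A rate titled 'due to toxicity' will be read as a measure of tolerability. That is the quantity Protocol 8.3.2.1 names in its safety analysis: "the proportion who stop treatment due to an inability to tolerate it". Under the SAP's rule the rate can include patients who died of their tumour while a line was still running, even though the database says so. Tables 14.2.2.4.1 to 14.2.2.4.3 set groups side by side (two or fewer versus more lines, number of targeted therapies, second-line targeted therapy versus chemotherapy). If on-treatment tumour deaths are unevenly spread across these groups, part of an apparent toxicity difference would be a difference in disease course. A reader of those tables could not tell.

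**Working it through.** The plan states no figure for this quantity, so there is none to reproduce. The check sets the definition, the CRF codes and the table templates side by side.

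**Step 1. How a tumour death reaches the count.** The inputs are SAP 5.9.5, CRF Table 5 and CRF section 4.

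| What happens | Stop reason coded | Counted as toxicity? |
|---|---|---|
| Line stopped at progression, death later | Disease progression | No |
| Line still running at death, cause recorded as disease progression | Death | Yes |
| Line stopped and coded AE, the event being the malignancy itself | AE | Yes, if any site codes it so |

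The second row follows directly from the text. The third is only a possibility. Protocol section 7 (Serious adverse events) says that if the malignancy results in death, "then the event leading to death must be recorded as an adverse event, and as a grade 5 serious adverse event". That governs safety reporting; no text says how the stop reason is then coded.

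**Step 2. What the planned outputs separate.**

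- Tables 14.2.2.4.1 to 14.2.2.4.3: one template, with a yes/no row and a count per patient, both for the composite. AE and Death are not separated.
- Tables 14.3.1.7 and 14.3.1.8: AE and Death are separate reason rows, but only for the treatment at inclusion, and Death is not split by cause.
- SAP 5.7.2 with Tables 14.3.2.1 and 14.3.2.14: "At least one adverse event leading to permanent discontinuation of treatment" and, in 5.7.2 and Table 14.3.2.1, the related-AE version. These are by treatment and do not use the Death code.
- Tables 14.2.2.2.1.8 and 14.2.2.2.1.9: stop reasons for targeted therapy by line number and by two or fewer versus more lines. There is an AE row and no Death row, and pre-inclusion lines are included.
- Table 14.2.2.5.1: stop reasons by main line and treatment group at inclusion. There is again an AE row and no Death row, over the entire follow-up.
- Table 14.1.3.4 and Listing 16.2.12: these use the cause of death but do not link it to the stop. Listing 16.2.5 gives the stop reason per line.

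So no planned table gives the AE/Death split, or the cause of those deaths, in the groups of Tables 14.2.2.4.1 to 14.2.2.4.3 for the post-inclusion period.

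**Step 3. Size per death.** One tumour death coded Death adds 1 to the number of discontinuations. It adds 100/N points to the patient rate of a group of N, or 0 points if that patient already has a counted AE stop. The documents give no sizes for these groups, so every N here is assumed:

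- N = 20: 100/20 = 5.0 points
- N = 35: 100/35 = 2.9 points
- N = 75: 100/75 = 1.3 points
- N = 130: 100/130 = 0.8 points

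The pairs 20/130 and 75/75 are an uneven and an even split of the planned 150 patients. They fit only the two-group Table 14.2.2.4.1; 35 is purely illustrative.

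**Step 4. Size for a group.** If A patients have AE stops and D other patients have Death stops, the composite rate is (A + D)/N, larger than the AE-only rate by the factor 1 + D/A. With assumed N = 75 and A = 10, the AE-only rate is 10/75 = 13.3%. D = 2 gives 12/75 = 16.0%, and D = 5 gives 15/75 = 20.0%. These counts are illustrations, not forecasts.

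**The case against.** The strongest reply is that little is hidden. The composite is spelled out in 5.9.5 and in both footnotes, the affected tables are descriptive additional analyses, and toxicity by treatment is reported properly elsewhere, including "at least one adverse event with a suspected relationship with the study treatment leading to permanent discontinuation of the treatment". AE stop reasons also appear in aggregate in groups close to those at issue. SAP 5.5.1 says treatment is changed after progression, so few patients may die of the tumour while a line is running.

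Most of this stands, and it limits the point. It does not remove it. A footnote that defines toxicity to include death from any cause discloses the composite but contradicts the title above it. The neighbouring tables cover other periods or other groups. SAP 5.5.1 also allows that some prevalent patients progressed without stopping, and Table 14.2.2.8.1 has a separate row for stopping after progression, so deaths on a continuing line are not excluded. Nor is this a worst-case rule for missing data like the one in 5.7.2: here the cause has its own CRF field.

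Three stronger readings are tempting and not supported:

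- **That all tumour deaths count as toxicity.** Only those whose line stop is coded Death are certain to; a line stopped for disease progression is not counted.
- **That the grade 5 reporting rule puts tumour deaths into the AE stops.** The documents do not say how sites code that stop.
- **That the split can be recovered only patient by patient from listings.** The tables in step 2 give part of it in aggregate.

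**Conclusion.** The definition is wrong as written: a stop coded Death with disease progression as its recorded cause is counted as toxicity. This rests on the SAP text and CRF fields alone. The consequence is modest. It is confined to the composite row of Tables 14.3.1.7 and 14.3.1.8, where AE and Death are also shown separately, and to Tables 14.2.2.4.1 to 14.2.2.4.3, where the composite stands alone. The number of affected deaths is unknown, possibly small or zero, and the direction of any distortion between groups cannot be stated. Progression-free and overall survival do not use this definition. The correction is worth making before the tables are produced because the needed field already exists.

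**What to change.** - **Definition.** In SAP 5.9.5 and both footnotes, count a Death stop as toxicity only when the end-of-study form gives the cause as an adverse event related to a study medication.
- **Tables 14.2.2.4.1 to 14.2.2.4.3.** Show AE stops and Death stops on separate rows, with Death split by recorded cause: progression, unrelated AE, related AE, missing. Label the AE row 'discontinuation for AE', because it still includes AEs unrelated to treatment.
- **Data review.** Check whether any fatal stop coded AE was the malignancy itself.
- **If the composite is kept.** Rename it 'discontinuation for AE or death from any cause'. This costs one line but leaves the rates unsplit.

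The cost is a short text change, a merge with an existing CRF field, one data-review check and a few extra rows in three tables. No new data are needed. The drawback is that some deaths may have no recorded cause and will sit in the missing row.

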5.9.6. Main Treatment Lines Received Over the Entire Follow-up Period

For each main treatment line, the number of main treatment lines, the nature of treatments, the duration and reasons for discontinuation will be presented over the entire follow-up (retrospective phase and prospective phase) overall and based on the current treatment at inclusion (targeted therapy/ chemotherapy / somatostatin analog).

The number of main treatment lines received during the study (quantitative and by class), the nature of lines of treatment received during the study (other than those received at inclusion) and the total number of treatment lines received will be shown based on the "at least one targeted therapy before inclusion (yes /no)" subgroup.

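### Toxicity stops after inclusion are tabulated per patient by total lines or total targeted therapies received, so the columns cannot be read as tolerance by line

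*SAP*

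**What the plan says.** SAP 5.9.5 sets the event and its window: "Discontinuation due to toxicity (AE or death) of the main treatment line will be described for the period after inclusion". It sets the unit: "The number of patients with at least one discontinuation due to toxicity and the number of discontinuations due to toxicity will be described". Two of its groupings are at issue here: "Number of lines for the entire follow-up", and "Number of targeted therapies received for the entire follow-up (0, 1, 2, >2".

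The templates in SAP 9.3.4 follow this. Table 14.2.2.4.1 has columns for ≤2 lines, >2 lines and total. Its first row is "Patients who have discontinued at least once due to toxicity", and its second is the number of such stops per patient. Its footnotes read "Discontinuation due to toxicity corresponds to discontinuation for an AE or Death" and "A patient may record several discontinuations due to toxicity". Table 14.2.2.4.2 reuses the template for 0, 1, 2 and >2 targeted therapies. Neither has a denominator of lines or of time on treatment.

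The grouping covers more than the study period. SAP 5.9.6 says that main lines "will be presented over the entire follow-up (retrospective phase and prospective phase", and a footnote to Table 14.2.2.2.1.5 likewise takes the entire follow-up as before and after inclusion. Lines before inclusion therefore count towards the column, but stops before inclusion do not count as events. Patients may enter on a first to fourth line and are followed for 24 months (SAP 3.3). SAP section 6 does not list this among the limitations.

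**The concern.** Two features make the columns hard to interpret. First, each further on-study line is another chance of a toxicity stop, so patients with many lines have had more chances. Second, the grouping looks forward. A patient included on a first line reaches >2 only after leaving two main lines, and leaving a line for an AE is one way to do so. Under SAP 4.7 an interruption of more than 3 months also splits one treatment into two lines, so a long stop can itself raise the count.

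Two other features work differently. Patients included on a third or fourth line sit in >2 with possibly one at-risk line. Death counts as toxicity, can occur only once and ends the sequence of lines, so it adds events to the low-line column.

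Discontinuations and their reasons belong to the safety part of the primary objective (Protocol 3.1, SAP 5.5). The study answers health-authority requests about two targeted therapies. A table that seems to show tolerance changing with the number of lines or targeted therapies could be quoted as a finding when it may only reflect how the columns were formed.

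**Working it through.** The documents give no expected rate of toxicity stops, so there is no planned figure to reproduce. The check asks what the template would show if toxicity were identical in every line.

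**Inputs from the documents.** 24 months after inclusion; entry on lines 1 to 4; stops counted after inclusion only; lines counted before and after inclusion; AE or death as the event.

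**Assumed inputs.** Each entry line 25%; the same constant stopping hazard in every line, median duration M = 12 months (6 as an alternative); 20% of stops for AE; 0% or 15% of stops by death; the next line starts at once after any other stop; no loss to follow-up.

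**Step 1: opportunity alone.** With probability p per line, the chance of at least one stop in k on-study lines is 1 − (1 − p)^k. For k = 1, 2, 3 this is 10/19/27% at p = 10%, 15/28/39% at 15% and 25/44/58% at 25%. This shows the mechanism but is not the ≤2 against >2 contrast.

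**Step 2: the SAP columns, AE stops only, M = 12.** Expected stops in 24 months: r = 24 × ln 2 / 12 = 1.386. So P(0 stops) = a = e^−r = 0.25, P(1) = b = r·e^−r = 0.3466, P(2 or more) = c = 0.4034.
- The ≤2 column holds entrants on line 1 with 0 or 1 stop and entrants on line 2 with none: 0.25 × (0.5966 + 0.25) = 0.2117 of patients.
- Its AE stops come only from line-1 entrants whose single stop was an AE: 0.25 × 0.2 × 0.3466 = 0.0173. Rate: 0.0173 / 0.2117 = **8.2%**.
- All patients: 1 − exp(−0.2 × 1.386) = 0.2421. The >2 column: (0.2421 − 0.0173) / (1 − 0.2117) = **28.5%**.

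Simulations of the same scenario gave 7.9% to 8.1% against 28.5% to 28.6%.

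**Step 3: AE or death, 15% of stops being deaths.** For line-1 entrants the share in ≤2 is L1 = a + 0.15(1 − a) + 0.85b + 0.85 × 0.15c, and the share in ≤2 with an event is E1 = 0.15(1 − a) + 0.2b + 0.85 × 0.15c. For line-2 entrants L2 = a + 0.15(1 − a) and E2 = 0.15(1 − a). Over all patients P = 1 − exp(−0.35r).
- M = 12: L1 = 0.7086, E1 = 0.2333, L2 = 0.3625, E2 = 0.1125, P = 0.3844. ≤2: 0.3458 / 1.0711 = **32.3%**. >2: (0.3844 − 0.0864) / (1 − 0.2678) = **40.7%**.
- M = 6 (r = 2.773, a = 0.0625, b = 0.1733, c = 0.7642): L1 = 0.4479, E1 = 0.2727, L2 = 0.2031, E2 = 0.1406, P = 0.6211. ≤2: 0.4133 / 0.6510 = **63.5%**. >2: (0.6211 − 0.1033) / (1 − 0.1627) = **61.8%**.

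Simulation gave 32.5% against 40.4%, and 64.5% against 61.5% (63.6% against 61.7% in a second run). In fifteen other combinations of entry mix and line duration, all with deaths counted, >2 was always the higher column. The contrasts ran from 49.4% against 51.9% to 23.4% against 48.0%.

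**Step 4: which denominator removes the artefact?**
- Dividing by on-study lines inside the same columns does not (AE only, M = 12). ≤2: 0.0693 / (0.25 + 2 × 0.3466 + 0.25) = 0.058 stops per line. >2: (0.2 × 1.386 − 0.0173) / (1 + 1.386 − 0.2983) = about 0.12.
- The percentage of all on-study lines stopped for AE, by line number, does not either. Later lines start late in a fixed 24-month window. With M = 6 and no deaths it fell in simulation from 19.1% at line 1 to 11.6% at line 6.
- The inclusion line only, by line number at inclusion, does: 0.2 × (1 − a) is 15.0% at M = 12 and 18.75% at M = 6, the same for every entry line.

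**The case against.** The best defence is that this is one of the additional analyses, worded as description, with no test. The protocol (8.3.2.1) and SAP 6.4 already say that strict treatment comparisons are not appropriate. Patients with at least one stop is a legitimate measure of cumulative burden. Much per-line information is also planned. Table 14.2.2.5.1 gives reasons for discontinuation by main line and treatment type, Table 14.2.2.2.1.8 does so for targeted therapy by line number, and Tables 14.3.1.7 and 14.3.1.8 cover the inclusion treatment with a toxicity row. All of this stands and limits the severity. None of these tables, however, gives toxicity stops of the inclusion line by line number at inclusion, and none corrects how the two tables would be read.

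A reader might also infer more than the documents support:
- That equal toxicity must produce a rising gradient, for instance 15/28/39% over one, two and three lines. Those figures ignore lines before inclusion and the counting of death; step 3 shows the sign can change.
- That a toxicity stop usually creates the next line. The CRF (section 3.3) provides for treatment abstention, and a death creates none.
- That the targeted-therapy table shows the same gradient. A patient with 0 targeted therapies may have had several other lines, and this grouping was not simulated.

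**Conclusion.** The point holds as a problem of interpretation. The two groupings depend partly on what follows a stop and differ in the number of at-risk lines, so differences between columns are not evidence about tolerance by line. For AE-only stops and the lines grouping, about 8% against 29% can arise with constant toxicity. For the SAP's AE-or-death outcome, the result runs from about 33% against 40% to a slight reversal at about 64% against 62%. Every size rests on assumed entry mix, line duration, AE share and death share, none of which the documents give. For the targeted-therapy grouping the concern is the same in kind but unquantified. The grouping by main treatment at inclusion in the same section is not affected. Severity: minor.

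**What to change.** Replace the two groupings in SAP 5.9.5 and Tables 14.2.2.4.1 and 14.2.2.4.2 with:

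(a) Toxicity stop of the inclusion line only, grouped by line number at inclusion and by number of targeted therapies received before inclusion. Both are known before the outcome. The flat result in step 4 assumes a hazard constant over time on the line, so show incident and prevalent patients separately, as SAP 5.7.1 already does for time to discontinuation.

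(b) Optionally, cumulative incidence of an AE stop from the start of each line, by line number at that start. Use delayed entry for prevalent patients, treat other stops including death as competing events, censor open lines and use patient-clustered confidence intervals.

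In either case show AE stops and death stops in separate rows. If the two tables are kept as they are, add a footnote that they show cumulative burden and not tolerance per line, and refer to Tables 14.2.2.5.1 and 14.3.1.7.

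The cost is a few re-specified rows in an additional descriptive analysis. Listing 16.2.5 already holds line number, start date, stop date and reason. The drawback of (a) is that it leaves out toxicity stops in later lines; (b) recovers the AE stops among them at the price of more programming.
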